**Visit 1**

Post-Vaccination Day (Date (dd/MM/yyyy))	Day 1 (Day of vaccination)	Day 2	Day 3	Day 4	Day 5	Day 6	Day 7	Day 8
Oral Temperature °F	/ /	/ /	/ /	/ /	/ /	/ /	/ /	/ /
General Systemic Symptoms: Grade 0 = None								
Chills/Shivering	Grade 1 = Mild (noticeable but does not interfere with activity) Grade 2 = Moderate (interferes with activity but did not need a medical visit or absenteeism [i.e. missing work or school]) Grade 3 = Severe (prevents daily activity and/or resulted in medical visit and/or absenteeism [i.e. missing work or school])							
Fatigue								
Body Aches								
Headache								
Joint pain								
Nausea								
Vomiting								
Diarrhea								
Abdominal Pain								
Body rash								

CISA TDAP/IIV Data Collection Form  
Memory Aid Simultaneous Group  
TT07A

Subject ID: \_\_\_\_\_

Flu Vaccine Local Vaccination Site Reactions:  RIGHT ARM  LEFT ARM								
	Grade 0 = None							
	Grade 1 = Mild (noticeable but does not interfere with activity)							
	Grade 2 = Moderate (interferes with activity but did not need a medical visit or absenteeism [i.e. missing work or school])							
	Grade 3 = Severe (prevents daily activity and/or resulted in medical visit and/or absenteeism [i.e. missing work or school])							
Pain								
Tenderness								
Swelling- size (mm)	mm	mm	mm	mm	mm	mm	mm	mm
Redness- size (mm)	mm	mm	mm	mm	mm	mm	mm	mm
Tdap Vaccine Local Site Reactions:  RIGHT ARM  LEFT ARM								
	Grade 0 = None							
	Grade 1 = Mild (noticeable but does not interfere with activity)							
	Grade 2 = Moderate (interferes with activity but did not need a medical visit or absenteeism [i.e. missing work or school])							
	Grade 3 = Severe (prevents daily activity and/or resulted in medical visit and/or absenteeism [i.e. missing work or school])							
Post-Vaccination Day	Day 1	Day 2	Day 3	Day 4	Day 5	Day 6	Day 7	Day 8
Pain								
Tenderness								
Swelling- size (mm)	mm	mm	mm	mm	mm	mm	mm	mm
Redness- size (mm)	mm	mm	mm	mm	mm	mm	mm	mm

CISA TDAP/IV Data Collection Form  
Memory Aid Simultaneous Group  
TT07A

Subject ID: \_\_\_\_\_

Other symptoms			

1 = Mild (noticeable but does not interfere with activity or measurement)  Grade 2 = Moderate (interferes with activity but did not need a medical visit or absenteeism [i.e. missing work or school])  Grade 3 = Severe (prevents daily activity and/or resulted in medical visit and/or absenteeism [i.e. missing work or school])
 
Other symptoms to report:  None
			
Symptom	Intensity: Mild, Moderate or Severe	Start date	Stop date

Medications					

New medications used following vaccination or changes to previously reported medications:  No  Yes (complete chart below)
					
Medication name	Dose	Frequency	Start date	Stop date	Reason

Any visit to the Emergency department (ED), Urgent Care, Labor and Delivery, or doctor's office other than routine check-up or prenatal visit?  No  Yes (please explain below and add dates of the visit to ED, Urgent Care, Labor and Delivery, or doctor's office)

---

---

---

Appendix C: Memory Aid for Sequential Group – Visit 1

CISA Tdap/IIV Data Collection Form  
Memory Aid Sequential Group  
T107B

Subject ID: -----

**Visit 1**

Please assess symptoms and fill out memory aid in the evening (after 4pm)

Post-Vaccination Day Date (dd/MM/yyyy) Oral Temperature °F	Day 1 (Day of vaccination)	Day 2	Day 3	Day 4	Day 5	Day 6	Day 7	Day 8
General Systemic Symptoms:								
Grade 0 = None								
Grade 1 = Mild (noticeable but does not interfere with activity)								
Grade 2 = Moderate (interferes with activity but did not need a medical visit or absenteeism [i.e. missing work or school])								
Grade 3 = Severe (prevents daily activity and/or resulted in medical visit and/or absenteeism [i.e. missing work or school])								
Chills/Shivering								
Fatigue								
Body Aches								
Headache								
Joint pain								
Nausea								
Vomiting								
Diarrhea								
Abdominal Pain								
Body rash								
Flu Vaccine Local Vaccination Site Reactions:  RIGHT ARM  LEFT ARM								
Grade 0 = None								
Grade 1 = Mild (noticeable but does not interfere with activity)								
Grade 2 = Moderate (interferes with activity but did not need a medical visit or absenteeism [i.e. missing work or school])								
Grade 3 = Severe (prevents daily activity and/or resulted in medical visit and/or absenteeism [i.e. missing work or school])								
Pain								
Tenderness								
Swelling- size (mm)	mm	mm	mm	mm	mm	mm	mm	mm
Redness- size (mm)	mm	mm	mm	mm	mm	mm	mm	mm

CISA TDAP/IV Data Collection Form  
Memory Aid Sequential Group  
T107B

Subject ID: \_\_\_\_\_

Other symptoms			
1 = Mild (noticeable but does not interfere with activity or measurement)			
Grade 2 = Moderate (interferes with activity but did not need a medical visit or absenteeism [i.e. missing work or school])			
Grade 3 = Severe (prevents daily activity and/or resulted in medical visit and/or absenteeism [i.e. missing work or school])			
Other symptoms to report:  None			
Symptom	Intensify: Mild, Moderate or Severe	Start date	Stop date

Medications					
New medications used following vaccination or changes to previously reported medications:  No  Yes (complete chart below)					
Medication name	Dose	Frequency	Start date	Stop date	Reason

Any visit to the Emergency department (ED), Urgent Care, Labor and Delivery, or doctor's office other than routine check-up or prenatal visit?  No  Yes (please explain below and add dates of the visit to ED, Urgent Care, Labor and Delivery, or doctor's office)

---

---

---

Appendix D: Memory Aid for Simultaneous Group – Visit 4

CISA Tdap/IIV Data Collection Form  
Memory Aid Simultaneous Group  
TI09A

Subject ID: -----

**Visit 4**

Please assess symptoms and fill out memory aid in the evening (after 4pm)

Post-Visit Day Date (dd/MM/yyyy) Oral Temperature °F	Day 1 (Day of visit)	Day 2	Day 3	Day 4	Day 5	Day 6	Day 7	Day 8
General Systemic Symptoms:								
Grade 0 = None								
Grade 1 = Mild (noticeable but does not interfere with activity)								
Grade 2 = Moderate (interferes with activity but did not need a medical visit or absenteeism [i.e. missing work or school])								
Grade 3 = Severe (prevents daily activity and/or resulted in medical visit and/or absenteeism [i.e. missing work or school])								
Chills/Shivering								
Fatigue								
Body Aches								
Headache								
Joint pain								
Nausea								
Vomiting								
Diarrhea								
Abdominal Pain								
Body rash								

CISA TDAP/IV Data Collection Form  
Memory Aid Simultaneous Group  
TT09A

Subject ID: -----

Other symptoms			
1 = Mild (noticeable but does not interfere with activity or measurement) Grade 2 = Moderate (interferes with activity but did not need a medical visit or absenteeism [i.e. missing work or school]) Grade 3 = Severe (prevents daily activity and/or resulted in medical visit and/or absenteeism [i.e. missing work or school]) Other symptoms to report:  None			
Symptom	Intensity: Mild, Moderate or Severe	Start date	Stop date

Medications					
New medications used following vaccination or changes to previously reported medications:  No  Yes (complete chart below)					
Medication name	Dose	Frequency	Start date	Stop date	Reason

Any visit to the Emergency department (ED), Urgent Care, Labor and Delivery, or doctor's office other than routine check-up or prenatal visit?  No  Yes (please explain below and add dates of the visit to ED, Urgent Care, Labor and Delivery, or doctor's office)

---

---

---

Appendix E: Memory Aid for Sequential Group – Visit 4

CISA Tdap/IIV Data Collection Form  
Memory Aid Sequential Group  
TI09B

Subject ID: \_\_\_\_\_

**Visit 4**

Please assess symptoms and fill out memory aid in the evening (after 4pm)

Post Vaccination Day Date (dd/MM/yyyy) Oral Temperature °F	Day 1 (Day of vaccination)	Day 2	Day 3	Day 4	Day 5	Day 6	Day 7	Day 8
General Systemic Symptoms: Grade 0 = None Grade 1 = Mild (noticeable but does not interfere with activity) Grade 2 = Moderate (interferes with activity but did not need a medical visit or absenteeism [i.e. missing work or school]) Grade 3 = Severe (prevents daily activity and/or resulted in medical visit and/or absenteeism [i.e. missing work or school])								
Chills/Shivering								
Fatigue								
Body Aches								
Headache								
Joint pain								
Nausea								
Vomiting								
Diarrhea								
Abdominal Pain								
Body rash								

CISA TDAP/IIV Data Collection Form  
Memory Aid Sequential Group  
T109B

Subject ID: \_\_\_\_\_

Tdap Vaccine Local Site Reactions:  RIGHT ARM  LEFT ARM	
Grade 0 = None	
Grade 1 = Mild (noticeable but does not interfere with activity)	
Grade 2 = Moderate (interferes with activity but did not need a medical visit or absenteeism [i.e. missing work or school])	
Grade 3 = Severe (prevents daily activity and/or resulted in medical visit and/or absenteeism [i.e. missing work or school])	
Pain	
Tenderness	
Swelling- size (mm)	mm mm mm mm mm mm mm mm mm mm
Redness- size (mm)	mm mm mm mm mm mm mm mm mm mm

**Other symptoms**  
1 = Mild (noticeable but does not interfere with activity or measurement)  
Grade 2 = Moderate (interferes with activity but did not need a medical visit or absenteeism [i.e. missing work or school])  
Grade 3 = Severe (prevents daily activity and/or resulted in medical visit and/or absenteeism [i.e. missing work or school])

Symptom	Intensity: Mild, Moderate or Severe	Start date	Stop date

**Medications**  
New medications used following vaccination or changes to previously reported medications:  No  Yes (complete chart below)

Medication name	Dose	Frequency	Start date	Stop date	Reason

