### **5.2.1 Randomization**

Participants will be randomized (1:1) to receive either IIV and Tdap simultaneously or sequentially (IIV followed by Tdap) using a permuted block randomization scheme stratified by Lead and Contributing sites. The project statistician at Duke University will generate permuted block randomization schemes which will be uploaded to REDCap. The randomization schedule will not be available to the study staff, so the next randomization allocation will not be known before randomization occurs. Following confirmation of study eligibility criteria during Visit 1, participant randomization will be through REDCap with treatment allocation recorded on the CRF.

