### **8.2 Sources of Material**

Medical history and immunization history will be obtained from the medical record and from patient report. Demographic information will be obtained from the medical record and patient report. Subjects will record solicited adverse reactogenicity events and any medical intervention sought on the day of and 7 days following vaccinations (or 7 days following mock vaccination) on the memory aid (Appendix B-E). Memory aid information will be reported to the study team during a telephone call or in the web-based REDCap system. The research staff will assess one or more of the following: weight, height, temperature, blood pressure, and pulse.

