## Appendix A: Memory Aid Instructions

### **HOW TO COMPLETE THE MEMORY AID**

#### **Completing the Memory Aid**

- Complete the Memory Aid every evening, starting the day of vaccination (Day 1) and continuing through Day 8. (Example: If you received your vaccination on Monday, you would start your memory aid Monday evening and finish your memory aid on the following Monday evening.)
- Assess symptoms and fill out the Memory Aid in the evening (after 4:00pm, but before midnight).
- For each symptom you experience, you must record the maximum severity and/or measurement.
- Fill out all the spaces each time. If you don't have any symptoms, write 0 in all the boxes.
- Record any other symptoms or medical problems that you have each day under the "other symptoms" portion of the Memory Aid.
- Record all new medications and any changes to previously reported medications that you take each day on page 3 of the Memory Aid.
  - You do not need to enter any regular medications you have already told us about. If you take a new medication, change a medication you were already on, or take something for comfort, please enter this information on the Memory Aid.
- Record any visits to the Emergency Room, Urgent Care, Labor and Delivery, or doctor's office (other than for a routine checkup or prenatal care) on the last page of the Memory Aid.
- Complete the Memory Aid for days 1-8 after vaccination.
- Be sure to return the paper Memory Aid to the study team at the next scheduled study visit.

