## Appendix F: Phone Script

## CISA TDAP/IIV Memory Aid Phone Script

To be used for visits: 2, 3, 5, 6, & 7

Hello, my name is \_\_\_\_\_ calling from the Tdap and Flu vaccine study at \_\_\_\_\_. I would like to review your memory aid information since your most recent study vaccination(s). This call should only take a few minutes. Is now a good time to review this information with you? Do you have your memory aid available to review with me?

Starting from day \_\_\_\_, please provide me with the temperatures that you recorded so far.

Starting with day \_\_\_\_, please tell me if you have recorded any reactions other than 0 (none). If so, in what category/ies? What number(s) did you record for the reactions? Did any of your symptoms prevent you from doing your daily activities or going to work/school?

Next on day \_\_\_\_, please tell me if you have recorded any reactions other than 0 (none). If so, in what category/ies? What number(s) did you record for the reactions? (*continue to ask for each day until all completed days have been reviewed with the subject*). Did any of your symptoms prevent you from doing your daily activities or going to work/school?

Did you report any other symptoms on your memory aid? Please provide me with the symptom, what you rated it, as well as the start and stop dates. (*continue to ask for any additional other symptoms*)

Did you take any new medications or change any of your current medications since you were vaccinated for the study? Please provide me with the medication name, dose, how often you took it, start and stop dates, and why you took the medicine.

Did you have any visits to the emergency room, urgent care, labor and delivery, or unplanned visits to the doctor's office, other than routine check-ups? If yes, please explain.

That concludes our study follow up call. Your next study visit is planned for: \_\_\_\_\_. Please remember to bring your memory aid with you to that visit so that we can place it in your study file.

Do you have any questions at this time? Please do not hesitate to contact the study team if you have any questions or concerns. We can be reached at \_\_\_\_\_.

Thank you for your continued study participation. Have a wonderful day.

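### As supplied, the sequential arm's Visit 4 diary (Appendix E) lacks the unscheduled-care question that Appendices B, C and D carry, and sequential women using REDCap may not be asked it by phone either

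*Combined protocol and SAP*

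**What the plan says.** Section 5.3 lists unscheduled medical care among the things assessed from vaccination day through Day 8 with the memory aid in Appendices B to E. Section 8.2 says the same aids record "any medical intervention sought on the day of and 7 days following vaccinations", and extends this to the mock week in the simultaneous arm. Appendix A instructs every participant: "Record any visits to the Emergency Room, Urgent Care, Labor and Delivery, or doctor's office", and says the place for this is the diary's final page.

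Appendices B, C and D each close with the matching item. In Appendix D, the simultaneous arm's Visit 4 diary, it reads "Any visit to the Emergency department (ED), Urgent Care, Labor and Delivery, or doctor's office other than routine check-up or prenatal visit". Appendix E, the sequential arm's Visit 4 diary, has systemic symptoms, Tdap site reactions, other symptoms and finally the medication table, "New medications used following vaccination or changes to previously reported medications". Appendix F follows.

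Appendix F, the phone script, asks "Did you have any visits to the emergency room, urgent care, labor and delivery, or unplanned visits" and is marked "To be used for visits: 2, 3, 5, 6, & 7". It does not distinguish between arms.

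**The concern.** The four diaries should differ only in which injection sites they ask about. Here the missing item follows the randomized arm. It is absent from the one diary that covers the sequential arm's week after Tdap, and present in the simultaneous arm's diary for the same calendar week, when those women received no vaccine. Section 5.1 (Visit 4) says the mock diary exists so that the two arms can be compared over that week, and a prompt given to one arm only works against that purpose.

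At stake is even ascertainment. Section 7.1.2 presents adverse events by treatment group, severity and relatedness. If a visit to care is less likely to come to light in one arm, events behind such visits may be under-recorded there, and the later analysis cannot separate that from a true difference.

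**Working it through.** The plan states no figure on this point, so there is none to reproduce. The check sets the forms and the other collection routes side by side.

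**Step 1. The diaries.**

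| Diary | Arm | Week covered | Care-visit question |
|---|---|---|---|
| Appendix B | Simultaneous | After IIV and Tdap (Visit 1) | Printed |
| Appendix C | Sequential | After IIV (Visit 1) | Printed |
| Appendix D | Simultaneous | After Visit 4, no vaccine | Printed |
| Appendix E | Sequential | After Tdap (Visit 4) | Absent in the text supplied |

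The item is one question per form, not a daily row, so the unit to count is the form. Simultaneous: 2 of 2. Sequential: 1 of 2. For the week after Tdap, the comparison is Appendix B (yes) against Appendix E (no). For the week after Visit 4, it is Appendix D (yes) against Appendix E (no).

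**Step 2. Other routes that could capture a visit in the sequential arm's week after Tdap.**

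- Phone script (Appendix F): asks the question. Visits 5 and 6 are the contacts that follow Visit 4.
- Table 2: medically-attended events are collected at Visits 1 to 8 with no arm restriction.
- Section 5.3: records of unscheduled appointments through Day 8 are obtained and reviewed.
- Visit 7 (Section 5.1): sequential women attend clinic, where staff review the diary and record adverse events. The text there ties the script to the simultaneous arm, although the script's own header names Visit 7 without restriction.
- Visit 8 (Section 5.1): electronic records are reviewed for maternal health events during the pregnancy.
- Appendix E keeps a medical visit as part of its Grade 3 definition. That grades a symptom; it does not record the visit itself.

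**Step 3. Who receives the Visit 5 and 6 calls.**

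- Section 5.1, Visits 5 and 6: staff contact participants using Appendix F. No exception is stated for REDCap users. The Visit 2 and 3 text, by contrast, has a separate paragraph for them.
- Section 5.3: contact at Visits 2-3 and 5-7 to go through the diary is described for paper users.
- Section 7.2: paper users are called at Visits 2, 3, 5 and 6; REDCap users are called if they fail to enter data.

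Under the first reading, every sequential woman is asked the scripted question after Tdap. Under the other two, a sequential woman who completes her REDCap entries on time need not be. The Protocol Summary describes the web and paper diaries as identical. If so, her web form would lack the question too, but the REDCap form is not shown.

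**Step 4. Size.** Let r be the share of sequential women who use REDCap and receive no call, p the proportion seeking unscheduled care in that week, and s the proportion of those whose visit is recorded anyway. The artificial shortfall in the sequential arm is r × p × (1 − s). The documents give none of the three. As a scale only: about 80 women randomized 1:1 is 80 / 2 = 40 per arm, so each sequential woman whose visit goes unrecorded moves that arm's proportion by 1 / 40 = 2.5 percentage points.

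**The case against.** The strongest reply has three parts.

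First, the item may be on the real form. Appendix E is the least cleanly extracted of the four diaries: its swelling and redness rows show ten cells for an eight-day diary, and it also lacks the tick-box line for no other symptoms that Appendices B to D carry. No page was removed between Appendix E and Appendix F, but that does not exclude text lost within a page. This stands, and it is why the source form must be checked before anything else.

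Second, the routes in Step 2 apply to both arms. This also stands. A reader might infer from the diaries that care after Tdap is solicited in the simultaneous arm only. The documents do not support that. Paper users, to whom the printed Appendix E certainly applies, are phoned under every reading of the protocol, and the delivery record review does not depend on self-report. That review may still miss outside care that the woman does not mention.

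Third, the analysis is descriptive. Section 7 says the pilot was not sized for group comparisons, and Section 7.1 specifies no comparison of medically-attended events as such. So a reader might infer a planned comparison that is biased by construction, and that too would go further than the text. What the plan does present by arm is adverse events, and these can be affected.

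A reader might also assume rates of care-seeking and unprompted reporting and apply them to all 40 sequential women to obtain a spurious difference in percentage points. That treats every sequential woman as unprompted, which the calls to paper users contradict, and it rests on rates found nowhere in the documents.

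**Conclusion.** In the supplied text, Appendix E does not match Appendices B, C and D, and it conflicts with Sections 5.3 and 8.2 and with Appendix A. The diary prompt for unscheduled care is on 2 of 2 forms in one arm and 1 of 2 in the other, and the form without it covers the week after Tdap. Because other routes reach both arms, the practical gap is narrower: chiefly sequential women using REDCap, and only if Sections 5.3 and 7.2 prevail over the Visit 5 and 6 text and the web form mirrors Appendix E. Any bias would be toward fewer recorded unscheduled visits and adverse events in the sequential arm; its amount cannot be estimated from the documents. The conclusion assumes that the item is truly missing from the source form. It is worth correcting because the difference follows the randomized arm and the remedy is small.

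**What to change.** 1. Check the source version of Appendix E and the REDCap version of the same form.
2. If the question is absent, add the one used in Appendices B to D to Appendix E, on paper and in REDCap.
3. Reconcile the Visit 5 and 6 text in Section 5.1 with Sections 5.3 and 7.2, stating whether REDCap users are asked the Appendix F care-visit question at those contacts.
4. For sequential women who have already completed Appendix E, ask the question at Visit 7 and confirm the answer from medical records before adverse events are presented by arm. Where Visit 7 has passed, the record review is what remains.

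The cost is one form revision with its REDCap field, an IRB notification of the revised memory aid, and a short retrospective check for completed diaries.

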## Appendix F: Phone Script

## CISA TDAP/IIV Memory Aid Phone Script

To be used for visits: 2, 3, 5, 6, & 7

Hello, my name is \_\_\_\_\_ calling from the Tdap and Flu vaccine study at \_\_\_\_\_. I would like to review your memory aid information since your most recent study vaccination(s). This call should only take a few minutes. Is now a good time to review this information with you? Do you have your memory aid available to review with me?

Starting from day \_\_\_\_, please provide me with the temperatures that you recorded so far.

Starting with day \_\_\_\_, please tell me if you have recorded any reactions other than 0 (none). If so, in what category/ies? What number(s) did you record for the reactions? Did any of your symptoms prevent you from doing your daily activities or going to work/school?

Next on day \_\_\_\_, please tell me if you have recorded any reactions other than 0 (none). If so, in what category/ies? What number(s) did you record for the reactions? (*continue to ask for each day until all completed days have been reviewed with the subject*). Did any of your symptoms prevent you from doing your daily activities or going to work/school?

Did you report any other symptoms on your memory aid? Please provide me with the symptom, what you rated it, as well as the start and stop dates. (*continue to ask for any additional other symptoms*)

Did you take any new medications or change any of your current medications since you were vaccinated for the study? Please provide me with the medication name, dose, how often you took it, start and stop dates, and why you took the medicine.

Did you have any visits to the emergency room, urgent care, labor and delivery, or unplanned visits to the doctor's office, other than routine check-ups? If yes, please explain.

That concludes our study follow up call. Your next study visit is planned for: \_\_\_\_\_. Please remember to bring your memory aid with you to that visit so that we can place it in your study file.

Do you have any questions at this time? Please do not hesitate to contact the study team if you have any questions or concerns. We can be reached at \_\_\_\_\_.

Thank you for your continued study participation. Have a wonderful day.

